A 24-month, single center, pilot, open label, controlled trial to evaluate the efficacy and safety of calcineurin-inhibitor reduction with conversion at 2 months to Reduced Dose tacrolimus/everolimus in adult renal transplant recipients following Campath® induction and steroid avoidance

NCT01935128

2/5/2018

A 24-month, single center, pilot, open label, controlled trial to evaluate the efficacy and safety of calcineurin-inhibitor reduction with conversion at 2 months to Reduced Dose tacrolimus/everolimus in adult renal transplant recipients following Campath® induction and steroid avoidance

Introduction

Campath-1H is a monoclonal antibody that was originally produced in a mouse against the human leukocyte antigen CD52.¹ CD52, a cell surface protein (antigen), is present on all lymphocytes and most monocytes. Campath-1H efficacy is related to its ability to cause profound depletion of T-lymphocytes long-term and B cell and monocyte depletion more transiently. Campath-1H not only depletes the blood of these cells, but it also penetrates to the lymphatic system to cause depletion there as well. Campath-1 was originally called Campath-1G (IgG2b) or Campath-1M (IgM) when it was a mouse antibody. It was genetically engineered so that the constant region of the mouse antibody was replaced with the human equivalent and it was renamed Campath-1H. Thus, Campath-1H only has mouse antibody segment at the binding site and the rest is of human origin; because of this, it is much less likely to elicit an anti-Campath® antibody response such as that which limits the re-use of OKT3® or Thymoglobulin®. In addition, because Campath-1H does not bind directly to the T-cell receptor (like OKT3®), it is much less likely to cause a cytokine release syndrome with a subsequent first dose reaction.

Background and Preliminary Data

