q. Compare the incidence of the development of donor specific antibody (DSA) in the first 24 months post-transplant in the experimental arm to the historical control arm.

Population:

Patients will include all patients age 18 or over who are receiving renal transplantation regardless of prior transplant, ECD kidney, living donor kidney, level of sensitization, or BMI.

Inclusion Criteria: At Screening: (2 months to 6 months after transplantation \pm 10 days)

- Male or female renal allograft recipients at least 18 years old.
- Patients who have given written informed consent to participate in the study. If consent cannot be expressed in writing, it must be formally documented and witnessed, ideally via an independent trusted witness.
- Patient who has received a kidney transplant from a deceased or living unrelated-/related donor.
- Recipient of a kidney allograft with a cold ischemia time (CIT) < 36 hours.
- Female patients must have a negative pregnancy test prior to study enrollment.
- Patients on CNI (tacrolimus and myfortic®) without steroid maintenance following Campath® induction.
- Patients with an acceptable allograft function defined by a serum creatinine < 2.5 mg/dL (250 μ mol/L) and an actual eGFR (MDRD4) \geq 30 mL/min/1.73m² (without renal replacement therapy).
- No evidence of rejection since the time of transplantation.

Exclusion criteria At Screening: (2 months to 6 months after transplantation \pm 10 days)

- Recipient of ABO incompatible allograft or a positive cross-match.
- Patient who is human immunodeficiency virus (HIV) positive.
- Patient who received an allograft from a Hepatitis B surface Antigen (HBsAg) or a Hepatitis C Virus (HCV) positive donor.

- HBsAg and/or a HCV positive patient with evidence of elevated LFTs (ALT/AST levels ≥ 2.5 times ULN). Viral serology results obtained within 6 months prior to screening are acceptable.
- Patient with severe restrictive (TLC $< 50\%$) or obstructive pulmonary (FEV1 < 50) disorders.
- Patient with severe allergy requiring acute (within 4 weeks of baseline) or chronic treatment that would prevent patient from potential exposure to everolimus, or with hypersensitivity to drugs similar to everolimus (e.g. macrolides).
- Patients with a known hypersensitivity/contraindication to any of the immunosuppressants or their classes, or to any of the excipients.

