- Patient with severe hypercholesterolemia (> 300 mg/dL) or hypertriglyceridemia (> 400 mg/dL) that cannot be controlled despite lipid lowering therapy.
- Patient with white blood cell (WBC) count $\leq 1,000$ /mm³ (and absolute neutrophil count of < 500) or a platelet count $\leq 50,000$ /mm³.
- History of malignancy of any organ system, treated or untreated, within the past 5 years, regardless of whether there is evidence of local recurrence or metastases. (Localized basal cell carcinoma of the skin at any time, or small (less than 4 cm) or low-grade renal cancers, bladder cancers or treated prostate cancer with no evidence of disease after 2 years are allowable)
- Graft loss.
- Patient on renal replacement therapy.
- Patient who experienced biopsy proven rejection.
- Proteinuria > 1 g/day (as calculated from the urinary protein-to-creatinine ratio). Protein-to creatinine ratios are only calculated if protein is 1+ or greater on urine dipstick as negative or trace amounts do not correlate to measurements near 1 g/day.
- Patients with recurrence of Focal Segmental Glomerulosclerosis (FSGS).
- Patient who has a current severe systemic infection according to the investigator judgment requiring continued therapy that would interfere with the objectives of the study.
- Patients with ongoing wound healing problems, clinically significant infection requiring continued therapy or other severe surgical complication in the opinion of the investigator.
- Presence of intractable immunosuppressant complications or side effects.
- Pregnant or nursing (lactating) women, where pregnancy is defined as the state of a female after conception and until the termination of gestation, confirmed by a positive serum human chorionic gonadotrophin laboratory test (> 5 mIU/mL)
- Women of child-bearing potential, defined as all women physiologically capable of becoming pregnant, including women whose career, lifestyle, or sexual orientation precludes intercourse with a male partner and women whose partners have been sterilized by vasectomy or other means, UNLESS they are using two birth control methods. The two methods can be a double barrier method or a barrier method plus a hormonal method.

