 - Adequate barrier methods of contraception include: diaphragm, condom (by the partner), intrauterine device (copper or hormonal), sponge or spermicide. Hormonal contraceptives include any marketed contraceptive agent that includes an estrogen and/or a progestational agent. Acceptable contraception methods will be discussed with all women of child-bearing potential.

- Reliable contraception should be maintained throughout the study and for 8 weeks after study drug discontinuation. For women who become pregnant while using Myfortic® or within 8 weeks of discontinuing therapy, we will report the pregnancy to the Mycophenolate Pregnancy Reference Registry ([name]) and will strongly encourage the patient to enroll in the pregnancy registry.
- Women are considered post-menopausal and not of child bearing potential if they have had 12 months of natural (spontaneous) amenorrhea with an appropriate clinical profile (e.g. age appropriate, history of vasomotor symptoms) or six months of spontaneous amenorrhea with serum FSH levels > 40 mIU/mL and estradiol < 20 pg/mL] or have had surgical bilateral oophorectomy (with or without hysterectomy) at least six weeks ago. In the case of oophorectomy alone, only when the reproductive status of the woman has been confirmed by follow up hormone level assessment is she considered not of child bearing potential.

Study Duration:

We plan to enroll 11 patients per year. Given this assumption, the enrollment will take five years. Adding two years of follow-up care, we will be able to complete the study in 7 years.

Study Design:

1. Single center pilot study utilizing historical control
2. A single treatment arm
3. Eleven patients per year
4. Five years to enroll 55 patients.
5. Enroll all patients who meet the inclusion criteria at 2 months and up to 6 months (± 10 days) post kidney transplantation and are willing to consent for this trial.
6. Patients would have study visits, serum creatinine measurements and other clinically relevant parameters measured monthly until 6 months, then q3 months until 2 years post-transplantation.
7. Graft survival would be measured by the absence of the need for dialysis.
8. It would not be mandatory, but a renal biopsy would be recommended at 2 years to look for underlying early signs of calcineurin toxicity/chronic allograft nephropathy.

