9. Secondary endpoints would include such parameters as post-transplant diabetes, proteinuria, lipid levels, mouth sores, neurotoxicity, pneumonitis, CMV, PTLN, BK-nephropathy, malignancies, cardiovascular complications, etc.
10. Our historical control will be composed of patients transplanted at the University of Toledo Medical Center between October 2011 and the beginning of this trial. All of those patients will have been treated with the exact same protocol as in this study except that they will not have been converted to the treatment arm above, but will have remained on tacrolimus and myfortic®, unless the clinical situation warranted changing immunosuppression. We expect that the control group will consist of approximately 50-55 patients and will have similar demographics to the patients that will be enrolled in this trial, given that we will use the same inclusion and exclusion criteria to select all patients from October 2011 until the start of this trial to populate

the historical control group. The reason for October 2011 as the starting point for the historical control is that this is the date when we modified our protocol to add a five day taper of steroids immediately after transplantation. Prior to that we only gave steroids immediately prior to the transplantation procedure. Thus, to be consistent with the patients in this trial, we believe the most accurate historical control should have the same treatment with steroids perioperatively. We will utilize all patients available in the historical control dataset and will not attempt to match for the demographics present in the experimental arm. The control group will consist of a historical control; prospective patients who are not willing to participate in the study will not be considered part of the control group.

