- unless diarrhea or leukopenia required lowering this dose. All patients would have received a five day taper of steroids at which time steroids were discontinued.
3. In this proposed pilot study, after two months of maintenance therapy of tacrolimus and myfortic® as described above, all patients will receive the following treatment: Their myfortic® will be weaned off quickly and everolimus initiated to achieve a target level of 3-8 ng/ml with a mean of 6 ng/ml. Once achieving a therapeutic dose of everolimus, the tacrolimus dose will be reduced to target a level of 3-5 ng/ml.

Detailed Renal Transplantation Immunosuppression and Management Protocol

1. The standard of care immunosuppressive regimen will be provided to all patients at the University of Toledo Medical Center for the first two months following renal transplantation. Beginning at 2 months (Screening) and not longer than 6 months (\pm 10 days) after renal transplantation, patients will be offered the opportunity to participate in a clinical trial to evaluate the efficacy and safety of calcineurin-inhibitor reduction. Informed consent will be obtained from all patients prior to enrollment. In addition, either at the time of evaluation for listing or actual listing on the deceased donor transplantation waiting list, patients will be counseled about immunosuppression trials being offered to patients undergoing renal transplantation at The University of Toledo Medical Center.
2. The initial standard of care immunosuppressive regimen for patients undergoing renal transplantation at The University of Toledo Medical Center consists of Campath® induction, myfortic® and methylprednisolone (Solu-medrol®) on call to the OR, with a five day steroid taper to no steroids by post-operative day five. Post-operatively patients will be maintained on tacrolimus (target level of 10 ng/ml) and myfortic® aiming for a dose of 540 mg PO BID with adjustment for diarrhea and leukopenia.
3. Patients are called to be admitted by the transplant coordinator after discussion with either the surgeon or nephrologists on call. Counseling about standard of care and investigational immunosuppressive regimens will be provided prior to proceeding with renal transplantation.

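### Historical controls have no set date within months 2 to 6 for applying the entry criteria, and the survival plan has no time origin or delayed entry, so staggered trial entry can bias the comparison in either direction

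*Combined protocol and SAP*

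**What the plan says.** **Trial entry.** Study Design item 5 reads "Enroll all patients who meet the inclusion criteria at 2 months and up to 6 months" after transplantation. Item 1 of the detailed management protocol reads "Beginning at 2 months (Screening) and not longer than 6 months". The headings of both criteria lists and the Screening column of the visit schedule give the same window, with a 10-day allowance. At that date the patient must meet "No evidence of rejection since the time of transplantation", and the exclusions include "Patient who experienced biopsy proven rejection" and graft loss. Some exclusions can clear with time, for example "Patients with ongoing wound healing problems, clinically significant infection requiring continued therapy".

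**Month-2 wording.** The title describes "calcineurin-inhibitor reduction with conversion at 2 months to Reduced Dose tacrolimus/everolimus in adult renal transplant recipients". Brief Immunosuppressive Management item 3 says that "after two months of maintenance therapy of tacrolimus and myfortic® as described above, all patients will receive the following treatment". Item 2 of the section on conversion at 2-6 months puts counselling and consent at the two-month mark. All of this describes trial patients, not controls.

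**Controls.** Study Design item 10 says "we will use the same inclusion and exclusion criteria to select all patients from October 2011 until the start of this trial to populate" the group, expects about 50 to 55 patients and rules out matching. It gives no assessment date.

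**Analysis.** The Statistical Section names Kaplan-Meier and Cox regression for variables such as graft survival. It states no origin, delayed entry or landmark. Objective 1 gives the co-primary composite (treated rejection, graft loss, death or loss to follow-up) no time point. Where outcomes are dated, they count from transplant: eGFR at 24 months in Objective 1, and follow-up to 2 years in Study Design item 6.

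**The concern.** A trial patient who enters at month 5 cannot have had a rejection or graft loss in months 2 to 5, because either event would have barred entry. A control accepted on month-2 status can have one. If both are then analysed from transplant with everyone at risk from the start, the late entrant is credited with guaranteed event-free time. Assessing controls at month 6 instead gives controls the credit relative to early trial entrants.

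The co-primary composite consists largely of events that can occur in these months. There is no randomisation and no matching, so shared eligibility criteria are the main stated ground for comparability, and their date matters. Control outcomes may already exist when the date is chosen. The Statistical Section also intends the data for meta-analysis, where sampling error shrinks but a shared bias does not.

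**Working it through.** **The plan's own figure.** The only design number is accrual: 11 per year x 5 years = 55 patients, and 5 + 2 = 7 years. It reproduces. The plan gives no figure for the point at issue, so the size below is illustrative.

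**Inputs, all from Background and Preliminary Data; none comes from this centre's current regimen with the steroid taper.**
- Centre's earlier tacrolimus/myfortic cohort (before the taper): rejection 15.6% at 12 months, 19.8% at 24. Nothing is given before month 12, so early timing is assumed.
- Campath arm of the randomised induction trial: 3% at 6 months, 5% at 12, 10% at 36. The 36-month rate is for low-risk patients only.
- Live-donor series on tacrolimus monotherapy: 1.0% at 1 and 3 months, 2.0% at 6, 9.0% at 12, 16.5% at 18, 19.5% at 24.

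**Method.** Assume no treatment effect and equal risk in early and late entrants. Take H(t) = -ln(1 - F(t)), linear between the quoted times. Someone event-free at entry time e has 24-month risk 1 - exp(-(H(24) - H(e))). Month-2 controls have e = 2. With even entry, trial survival is exp(-(H(24) - H(e))) averaged over e from 2 to 6.

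**Worked case, centre's earlier cohort.** H(2) = 0.0283, H(6) = 0.0848, H(24) = 0.2206.
- Month 2 to 6 risk: 1 - exp(-0.0565) = 5.5%.
- Month-2 controls: 1 - exp(-0.1924) = 17.5%.
- Trial, even entry: survival 0.825 x (exp(0.0565) - 1)/0.0565 = 0.849, so risk 15.1%.
- Difference: -2.4 points, or 1.3 of 55 patients.

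**All three curves, month-2 controls, time from transplant, no delayed entry** (SE for 55 v 50 patients):

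| Curve | Month 2-6 risk | Even entry | HR | SE | 70% at month 2, rest even |
|---|---|---|---|---|---|
| Live-donor series | 1.0% | -0.3 points (0.2 patients) | 0.98 | 7.6 | -0.1 |
| Randomised trial | 2.0% | -0.95 points (0.5 patients) | 0.85 | 4.7 | -0.3 |
| Centre's earlier cohort | 5.5% | -2.4 points (1.3 patients) | 0.84 | 7.2 | -0.7 |

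Pooling the randomised trial's 36-month rates by arm size, (164 x 10% + 70 x 18%)/234 = 12.4%, gives HR 0.87 in place of 0.85. As a scale, the shift with even entry is about 0.3 to 0.5 points per 1% of event risk in months 2 to 6.

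**Reverse case, controls assessed at month 6, centre's earlier rates.** Control risk is 1 - exp(-(0.2206 - 0.0848)) = 12.7%. The difference is 15.1 - 12.7 = +2.4 points with even trial entry, and 17.5 - 12.7 = +4.8 if all trial patients enter at month 2. If trial entry and control assessment are both at month 2, it is zero.

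**Composite, upper illustration.** Adding rejection, death-censored graft loss and death in the centre's earlier cohort with no overlap gives 15.6 + 10.6 + 4.2 = 30.4% at 1 year and 19.8 + 14.4 + 9.4 = 43.6% at 2 years. With even entry and month-2 controls this yields -3.8 points (HR 0.86, 2.1 patients, SE 9.5). Loss to follow-up is left out.

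**Does delayed entry remove it?** Simulations used 1,000,000 patients per arm and a true HR of 1.
- Falling (Weibull) hazard through 15.6% and 19.8%, even entry: HR 0.81 without delayed entry, 1.00 with it.
- 20% of patients reversibly ineligible at month 2, clearing evenly over months 2 to 7, with doubled hazard, across the three curves and both entry patterns: month-2 controls without delayed entry, HR 0.95 to 1.14; month-2 controls with delayed entry, 1.12 to 1.16; controls entering on their first eligible date, 0.99 to 1.00.

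The last comparison shows why the control's entry date matters as well as the clock.

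**The case against.** The strongest reply is that month-2 controls combined with spread-out trial entry applies a different reading of the protocol to each group. If the two-month wording governs, trial patients enter at month 2 and there is no bias against month-2 controls. If the 2 to 6 month window governs, the shared criteria carry it to controls too. This largely stands. A reader might infer that controls have no window at all, or that the plan adopts month-2 controls. The documents support neither: the window is inherited, and the month-2 passages concern trial patients. What remains is that a window is not a date, and a control without a screening visit needs one.

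It is also fair to say that harm requires several unstated choices together (a fixed control date, material late entry, a transplant clock, no delayed entry), and that Objective 1b and Study Design item 6 settle the clock only for eGFR and visits. The shift is small beside the standard error. The Study Purpose calls the comparisons descriptive, and the Statistical Section says the study is unpowered and weakened by its historical control. Those statements excuse imprecision. They do not address a systematic shift that one paragraph can prevent.

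Finally, some criteria rest on investigator judgement, so first eligible dates read from charts will be approximate. That stands as a cost of the fix.

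**Conclusion.** The gap is real and is rated minor to should-fix. The plan allows staggered, event-free entry, gives controls no date within the same window, and names survival methods without an origin or delayed entry. A single fixed control date with time from transplant would then bias the comparison with no treatment effect present.

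A reader might infer that the plan favours everolimus. The documents do not establish that. Month-2 controls favour everolimus, month-6 controls favour control, and higher risk among late entrants can offset or reverse the first. No passage adopts a biased analysis.

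For rejection, the illustrative size is 0.3 to 2.4 points at 24 months with even entry and month-2 controls, 0.1 to 0.7 points if 70% enter at month 2, and 2.4 to 4.8 points the other way with month-6 controls and the centre's earlier rates. The composite figure of 3.8 points is an upper illustration. All of these rest on assumed entry patterns and borrowed rates. The Background reports lower rejection at this centre since the taper was added, so the centre should rescale using month 2 to 6 event rates from its own charts.

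**What to change.** Before control outcomes are examined, add one paragraph to the Statistical Section:

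- For graft survival and the composite, the origin is the transplant date with delayed entry. Each trial patient enters the risk set at enrolment. Each control enters on the first date within months 2 to 6 on which all chart-assessable criteria are met.
- Use start-stop Cox regression and left-truncated Kaplan-Meier curves, with numbers at risk shown.
- As one sensitivity analysis, use a common month-6 landmark in both groups and report earlier events separately.
- Use the same control set for 24-month eGFR.
- Report the distribution of trial entry times.

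Also reconcile two pairs of passages: the two-month counselling and consent wording (item 2 of the conversion section) with the 2 to 6 month window used elsewhere; and follow-up to 2 years after transplant (Study Design item 6) with the visit schedule, which lists 24 treatment-period months after a Screening visit at months 2 to 6.

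The cost is re-screening 50 to 55 control charts over months 2 to 6. First eligible dates will be imprecise where criteria need judgement, and early estimates will be unstable if few trial patients are at risk just after month 2. No new patients or visits are needed.
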